5. VARIABLES AND THEIR ASSESSMENT

5.1 EFFICACY

5.1.1 Endpoints of efficacy

The primary endpoint for this trial is a safety endpoint. See [section 5.2.1](#). There are no primary efficacy endpoints.

The secondary efficacy endpoints (all time to first event) are:

1. A combined endpoint of thrombotic events or death (DTE: all death + MI + stroke/SE) and unplanned revascularisation by PCI/CABG
2. A combined endpoint of thrombotic events or death (DTE: all death + MI + stroke/SE)
3. Individual outcome events:
 - All death
 - Cardiovascular death
 - Non-cardiovascular death
 - Undetermined
 - MI
 - Stroke
 - SE
 - Stent thrombosis
4. Composite endpoint of death + MI + stroke
5. Unplanned revascularisation by PCI/CABG

See [Section 7.3.1](#) for details of the analyses.

5.1.2 Assessment of efficacy

These endpoints will be adjudicated by the IAC using criteria outlined in its charter governing the adjudication process.

5.1.2.1 Death

Death from any cause includes cardiovascular death, non-cardiovascular-death and undetermined cause of death, as classified by adjudication [[R13-4874](#), [R15-0010](#)].

Cardiovascular death

Cardiovascular (CV) death is defined as death due to any cause related to the heart or blood vessels, including myocardial infarction, stroke, aortic dissection, pulmonary embolism, deep vein thrombosis, and other cardiovascular causes, as classified by adjudication [[R13-4874](#), [R15-0010](#)].

Proprietary confidential information.

© 2016 Boehringer Ingelheim International GmbH or one or more of its affiliated companies. All rights reserved.

This document may not - in full or in part - be passed on, reproduced, published or otherwise used without prior written permission.

Non-cardiovascular death

?, * @ +%)#\$(+%"*%) () *3 +%)#\$\$' \$) (5%/'"/ /)1(%#\$)#(*,# #\$,12\$##, 8% /)&+',0)/(17)&' * *)#1&%(4 7'(#%)8,0%; A\$(%)&5,((87%%B)957%α' *, * @ /)1(%(, " +%)#\$\$C

- Pulmonary
- Renal
- Gastrointestinal
- Hepatobiliary
- Pancreatic
- Infection (includes sepsis)
- Inflammatory (e.g., Systemic Inflammatory Response Syndrome (SIRS) / Immune (including autoimmune)
- Haemorrhage that is neither cardiovascular bleeding or a stroke
- Non-CV procedure or surgery
- Trauma
- Suicide
- Non-prescription drug reaction or overdose
- Prescription drug reaction or overdose
- Neurological (non-cardiovascular)
- Malignancy
- Other non-CV (to be specified)

Undetermined Cause of Death

Undetermined cause of death refers to a death not attributable to one of the above categories of CV death or to a non-CV cause. Inability to classify the cause of death may be due to lack of information (e.g., the only available information is “patient died”) or when there is insufficient supporting information or detail to assign the cause of death. In general, most deaths should be classifiable as CV or non-CV and therefore the use of this category of undetermined cause of death should apply to few patients only.

Further details on death classification will be specified in the adjudication charter.

5.1.2.2 Myocardial infarction

Criteria for acute MI [R13-4872]:

The term acute MI should be used when there is evidence of myocardial necrosis in a clinical setting consistent with acute myocardial ischaemia.

Under these conditions any one of the following criteria meets the diagnosis for MI:

Proprietary confidential information.

© 2016 Boehringer Ingelheim International GmbH or one or more of its affiliated companies. All rights reserved.

This document may not - in full or in part - be passed on, reproduced, published or otherwise used without prior written permission.

- Detection of a rise and/or fall of cardiac biomarker values [preferably cardiac troponin (cTn)] with at least one value above the 99th percentile upper reference limit (URL) and with at least one of the following:
 - Symptoms of ischaemia
 - New or presumed new significant ST-segment–T wave (ST–T) changes or new left bundle branch block (LBBB)
 - Development of pathological Q waves in the ECG
 - Imaging evidence of new loss of viable myocardium or new regional wall motion abnormality
 - Identification of an intracoronary thrombus by angiography or autopsy
- Cardiac death with symptoms suggestive of myocardial ischaemia and presumed new ischaemic ECG changes or new LBBB, but death occurred before cardiac biomarkers were obtained, or before cardiac biomarker values would be increased
- PCI related MI is arbitrarily defined by elevation of cTn values $> 5 \times$ 99th percentile URL in patients with normal baseline values (\leq 99th percentile URL) or a rise of cTn values $\geq 20\%$ if the baseline values are elevated and are stable or falling. In addition, either (i) symptoms suggestive of myocardial ischaemia or (ii) new ischaemic ECG changes or (iii) angiographic findings consistent with a procedural complication or (iv) imaging demonstration of new loss of viable myocardium or new regional wall motion abnormality are required
- Stent thrombosis associated with MI when detected by coronary angiography or autopsy in the setting of myocardial ischaemia and with a rise and/or fall of cardiac biomarker values with at least one value above the 99th percentile URL
- CABG related MI is arbitrarily defined by elevation of cardiac biomarker values ($> 10 \times$ 99th percentile URL) in patients with normal baseline cTn values (\leq 99th percentile URL). In addition, either (i) new pathological Q waves or new LBBB, or (ii) angiographic documented new graft or new native coronary artery occlusion, or (iii) imaging evidence of new loss of viable myocardium or new regional wall motion abnormality.

Criteria for fatal MI

Death due to Acute MI refers to a death by any cardiovascular mechanism (e.g., arrhythmia, sudden death, heart failure, stroke, pulmonary embolus, peripheral arterial disease) ≤ 30 days after a MI related to the immediate consequences of the MI, such as progressive heart failure or recalcitrant arrhythmia. Acute MI (for criteria see above) should be verified to the extent possible by the diagnostic criteria outlined for acute MI or by autopsy findings showing recent MI or recent coronary thrombosis. Death resulting from a procedure to treat a MI (e.g.

Proprietary confidential information.

© 2016 Boehringer Ingelheim International GmbH or one or more of its affiliated companies. All rights reserved.

This document may not - in full or in part - be passed on, reproduced, published or otherwise used without prior written permission.

PCI, CABG), or to treat a complication resulting from MI, should also be considered death due to acute MI [[R15-0010](#)].

Silent MI

Silent myocardial infarction will be retrospectively diagnosed by the appearance of significant new Q-waves on an ECG performed after randomisation. In such cases, the date of the event is recorded as the midpoint between the ECG with new Q-waves and the prior normal ECG.

Criteria for prior MI [[R13-4872](#)]:

Any one of the following criteria meets the diagnosis for prior MI:

- Pathological Q waves with or without symptoms in the absence of non-ischaemic causes
- Imaging evidence of a region of loss of viable myocardium that is thinned and fails to contract, in the absence of a non-ischaemic cause
- Pathological findings of a prior MI.

5.1.2.3 Stroke

Stroke is defined as an acute episode of focal or global neurological dysfunction caused by brain, spinal cord, or retinal vascular injury as a result of haemorrhage or infarction [[DEF@GHI@R15-0010J](#)].

Ischaemic Stroke

Ischaemic stroke is defined as an acute episode of focal cerebral, spinal, or retinal dysfunction caused by infarction of central nervous system tissue. Haemorrhage may be a consequence of ischaemic stroke. In this situation, the stroke is an ischaemic stroke with haemorrhagic transformation and not a haemorrhagic stroke.

Haemorrhagic stroke

Haemorrhagic stroke is defined as an acute episode of focal or global cerebral or spinal dysfunction caused by intraparenchymal, intraventricular, or subarachnoid haemorrhage.

Undetermined Stroke

Undetermined stroke is defined as an acute episode of focal or global neurological dysfunction caused by presumed brain, spinal cord, or retinal vascular injury as a result of haemorrhage or infarction but with insufficient information to allow categorisation as ischaemic or haemorrhagic stroke.

Proprietary confidential information.

© 2016 Boehringer Ingelheim International GmbH or one or more of its affiliated companies. All rights reserved.

This document may not - in full or in part - be passed on, reproduced, published or otherwise used without prior written permission.

Fatal stroke

Fatal stroke is defined as death from any cause within 30 days of stroke.

Severity of recurrent stroke

Severity of recurrent stroke will be assessed by modified Rankin Scale (mRS) at the onset of stroke and at 3 months after recurrent stroke, if this time frame falls anytime within the study participation. Disabling stroke is defined as a stroke with mRS ≥ 4 at 3 months (see [Appendix 10.3](#) for definition of mRS).

5.1.2.4 Systemic embolism

SE is an acute vascular occlusion of the extremities or any organ (kidneys, mesenteric arteries, spleen, retina or grafts) and must be documented by angiography, surgery, scintigraphy or autopsy.

5.1.2.5 Stent Thrombosis

There will be three categories of evidence to define stent thrombosis:

1. Definite Stent Thrombosis

A definite stent thrombosis is considered to have occurred by either angiographic or pathological confirmation [[R13-4874](#), [R15-0010](#)]:

- Angiographic confirmation of stent thrombosis¹
 - The presence of a thrombus² that originates in the stent or in the segment 5 mm proximal or distal to the stent and presence of at least 1 of the following criteria within a 48-hour time window:
 - Acute onset of ischaemic symptoms at rest
 - New ischaemic ECG changes that suggest acute ischaemia
 - Typical rise and fall in cardiac biomarkers (refer to definition of spontaneous MI)
 - Non-occlusive thrombus

Intracoronary thrombus is defined as a (spheric, ovoid, or irregular) non-calcified filling defect or lucency surrounded by contrast material (on 3 sides or within a coronary stenosis) seen in multiple projections, or persistence of

¹ The incidental angiographic documentation of stent occlusion in the absence of clinical signs or symptoms is not considered a confirmed stent thrombosis (silent occlusion).

² Intracoronary thrombus

contrast material within the lumen, or a visible embolization of intraluminal material downstream

- Occlusive thrombus

Thrombolysis In Myocardial Infarction (TIMI) 0 or TIMI 1 intrastent or proximal to a stent up to the most adjacent proximal side branch or main branch (if originates from the side branch).

- Pathological Confirmation of Stent Thrombosis

Evidence of recent thrombus within the stent determined at autopsy or via examination of tissue retrieved following thrombectomy.

2. Probable Stent Thrombosis

Clinical definition of probable stent thrombosis is considered to have occurred after intracoronary stenting in the following cases:

- Any unexplained death within the first 30 days
- Irrespective of the time after the index procedure, any MI that is related to documented acute ischaemia in the territory of the implanted stent without angiographic confirmation of stent thrombosis and in the absence of any other obvious cause

3. Possible Stent Thrombosis

Clinical definition of possible stent thrombosis is considered to have occurred with any unexplained death from 30 days after intracoronary stenting until end of trial follow-up.

5.1.2.6 Repeated revascularisation by PCI/CABG

Repeated revascularisation due to objectively documented recurrent ischaemia, stent thrombosis or ACS. Unplanned revascularisation is any repeated revascularisation not planned prior to informed consent. These cases will undergo adjudication for confirmation of whether the event was unplanned, the type of procedure, the indication and if it is a target lesion revascularisation.

All details of documentation required for adjudication will be provided in the ISF.

5.2 SAFETY

5.2.1 Endpoints of safety

The primary endpoint for this trial is time to first ISTH MBE or CRNMBE. For definition of CRNMBE see [section 5.2.2.1](#).

Proprietary confidential information.

© 2016 Boehringer Ingelheim International GmbH or one or more of its affiliated companies. All rights reserved.

This document may not - in full or in part - be passed on, reproduced, published or otherwise used without prior written permission.

Other safety endpoints are:

1. Major bleeding (ISTH)
2. CRNMBE (for definition see [section 5.2.2.1](#))
3. Clinically relevant bleeding measured using the following definitions:
 - Bleeding Academic Research Consortium (BARC) ≥ 3
 - TIMI group - Major and Minor
4. Minor and total bleeding (ISTH, BARC and TIMI)
5. Intracranial haemorrhage

5.2.2 Assessment of adverse events

5.2.2.1 Assessment of Bleeding events

Patients should be carefully assessed for signs and symptoms of bleeding. Bleeding will be classified as major, Clinically Relevant Non Major Bleeding Event (CRNMBE) or minor. Major bleeds will be further sub classified as life-threatening and other major bleeds. The location of the bleeding including the specific critical area or organ into which the bleeding occurred and whether or not it prolongs hospitalisation will be recorded. The following definitions are specified for bleeds:

Definition of a major bleed

Major bleeds will be defined according to the ISTH definition of a major bleed, as follows [[R05-0344](#)].

- Symptomatic bleeding in a critical area or organ, such as intracranial, intraspinal, intraocular, retroperitoneal, intra-articular or pericardial, or intramuscular with compartment syndrome

and/or

- Bleeding associated with a reduction in haemoglobin of at least 2g/dL (1.24mmol/L), or leading to transfusion of two or more units of blood or packed cells¹

and/or

- Fatal bleed

Definition of a CRNMBE

A clinically relevant non-major bleeding event is a clinically overt bleed that does not meet

¹ Bleeding should be overt and the haemoglobin drop should be considered to be due to and temporally related to the bleeding event.

the criteria for a major bleed but prompts a clinical response, in that it leads to at least one of the following:

- A hospital admission for bleeding
- or
- A physician guided medical or surgical treatment for bleeding
- or
- A physician guided change, interruption¹ or discontinuation of study drug.

Definition of a minor bleed

Minor bleeds are clinical bleeds that do not fulfil the criteria for major bleeds. Minor bleeds will be further divided to those that are CRNMBE, (see above) and those that are not.

Definition of a life-threatening bleed

Major bleeds are to be classified as life-threatening if they meet one or more of the following criteria:

- Fatal, or symptomatic intracranial bleed; reduction in haemoglobin of at least 5g/dL; transfusion of at least four units of blood or packed cells, associated with hypotension requiring the use of i.v. inotropic agents; necessitated surgical intervention.

Definition of intracranial haemorrhage (ICH)

Intracranial haemorrhage (ICH) comprises the subtypes of intracerebral bleeds, subdural bleeds, epidural bleeds and subarachnoid bleeds and will be recorded.

Definition of a fatal bleeding

Fatal bleeding is defined as a bleeding event that the IAC determines is the primary cause of death or contributes directly to death.

Total bleeds

This is the sum of all major and minor bleeds.

In addition to the specified primary definition to be used for major bleeds in this trial (according to ISTH criteria, see above), components of the further bleeding definitions will be prospectively collected. It will be the responsibility of the IAC to categorise investigator-reported bleeding events according to the following pre-specified secondary classifications:

- **BARC** ([R13-4065](#), [R13-4066](#))
- **TIMI** ([P07-10190](#))

TIMI Classification of Bleeding

¹ Interruption of study drug (more than omitting one dose) due to the bleeding event.

The TIMI definition of bleeding uses four categories: major, minor, minimal and none, with definitions of the first three as follows:

- Major
Intracranial haemorrhage or a ≥ 5 g/dL decrease in haemoglobin concentration or a $\geq 15\%$ absolute decrease in haematocrit
- Minor
Observed blood loss: ≥ 3 g/dL decrease in haemoglobin concentration or $\geq 10\%$ decrease in haematocrit.
No observed blood loss: ≥ 4 g/dL decrease in haemoglobin concentration or a $\geq 12\%$ decrease in haematocrit
- Minimal
Any clinically overt sign of haemorrhage (including imaging) associated with a < 3 g/dL decrease in haemoglobin concentration or $< 9\%$ decrease in haematocrit.

BARC Definition for Bleeding¹

Type 0: no bleeding

Type 1: bleeding that is not actionable and does not cause the patient to seek unscheduled performance of studies, hospitalisation, or treatment by a healthcare professional; may include episodes leading to self-discontinuation of medical therapy by the patient without consulting a healthcare professional

Type 2: any overt, actionable sign of haemorrhage (e.g., more bleeding than would be expected for a clinical circumstance, including bleeding found by imaging alone) that does not fit the criteria for type 3, 4, or 5 but does meet at least one of the following criteria: (1) requiring nonsurgical, medical intervention by a healthcare professional, (2) leading to hospitalisation or increased level of care, or (3) prompting evaluation

Type 3:

- Type 3a
 - Overt bleeding plus haemoglobin drop of 3 to < 5 g/dL* (provided haemoglobin drop is related to bleed)
 - Any transfusion with overt bleeding

¹ Footnotes to BARC definition:

CABG indicates coronary artery bypass graft. Platelet transfusions should be recorded and reported but are not included in these definitions until further information is obtained about the relationship to outcomes. If a CABG-related bleed is not adjudicated as at least a type 3 severity event, it will be classified as not a bleeding event. If a bleeding event occurs with a clear temporal relationship to CABG (i.e., within a 48-h time frame) but does not meet type 4 severity criteria, it will be classified as not a bleeding event.

*Corrected for transfusion (1 U packed red blood cells or 1 U whole blood = 1 g/dL haemoglobin).

†Cell saver products are not counted.

Proprietary confidential information.

© 2016 Boehringer Ingelheim International GmbH or one or more of its affiliated companies. All rights reserved.

This document may not - in full or in part - be passed on, reproduced, published or otherwise used without prior written permission.

- Type 3b
 - Overt bleeding plus haemoglobin drop ≥ 5 g/dL* (provided haemoglobin drop is related to bleed)
 - Cardiac tamponade
 - Bleeding requiring surgical intervention for control (excluding dental/nasal/skin/haemorrhoid)
 - Bleeding requiring i.v. vasoactive agents
- Type 3c
 - Intracranial haemorrhage (does not include microbleeds or haemorrhagic transformation, does include intraspinal)
 - Subcategories confirmed by autopsy or imaging or lumbar puncture
 - Intraocular bleed compromising vision

Type 4: CABG-related bleeding

- Perioperative intracranial bleeding within 48 hour
- Reoperation after closure of sternotomy for the purpose of controlling bleeding
- Transfusion of ≥ 5 U whole blood or packed red blood cells within a 48-hour period†¹
- Chest tube output ≥ 2 L within a 24-hour period

Type 5: fatal bleeding

- Type 5a
 - Probable fatal bleeding; no autopsy or imaging confirmation but clinically suspicious
- Type 5b
 - Definite fatal bleeding; overt bleeding or autopsy or imaging confirmation

The protocol specified study definitions will be used by the Adjudication Committee as outlined in its Charter governing the adjudication process.

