3.3.4 Removal of patients from therapy or assessments

3.3.4.1 Removal of individual patients

An individual patient is to be withdrawn from the trial if:

- The patient withdraws consent, without the need to justify the decision

Treatment with study drugs should be discontinued if:

- The patient needs to take concomitant drugs that interfere with the investigational product or other study medication(s)
- The patient is no longer able to take trial medication for other medical reasons (e.g. surgery, AEs, or other diseases)
- The patient is persistently noncompliant with study drug administration
- If a patient becomes pregnant during the trial the investigational drug will be stopped, the patient will be discontinued from the trial medication and the patient will be followed up until birth or otherwise termination of the pregnancy. For further

Proprietary confidential information.

© 2016 Boehringer Ingelheim International GmbH or one or more of its affiliated companies. All rights reserved.

This document may not - in full or in part - be passed on, reproduced, published or otherwise used without prior written permission.

information, including the process for follow-up on the outcome of the pregnancy please see [Section 5.2.2.3](#).

- Patients on dabigatran etexilate who are found to have a CrCl <30mL/min during the course of the trial, should have study medication stopped and a parenteral anticoagulant can be started according to local practice (see [Appendix 10.1](#) for switching to a parenteral anticoagulant). CrCl laboratory testing should be repeated as soon as feasible, ideally within 48 hours. If this second measurement confirms a CrCl <30mL the patient should be permanently discontinued from dabigatran etexilate, unless the concomitant clinical condition is expected to allow recovery of the renal function within 7 days from the initial CrCl reduction. A patient should also be permanently discontinued from study drug, if CrCl drops to <30mL/min at two different occasions during the trial
- In the opinion of the Investigator, continuation on the study drug is not in the patient's best interest, if eligibility criteria are being violated, or if the patient fails to comply with the protocol (e.g. non-attendance at trial assessments)
- The patient elects to stop taking study drug (the patient should be encouraged to resume study drug per the protocol).

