All patients will also take clopidogrel (75mg q.d.) or ticagrelor (90mg b.i.d.) according to the local label for at least 12 months after randomisation (in addition to either dabigatran etexilate or warfarin). After 12 months of treatment the clopidogrel or ticagrelor can be discontinued or switched to ASA (≤ 100 mg q.d.) at the discretion of the Investigator.

For patients randomised to receive warfarin:

Patients randomised to receive warfarin will receive ASA (≤ 100 mg q.d.) for either one month in patients with a BMS and for three months in patients with a DES.

Warfarin and dabigatran etexilate supplies will be managed using the IRT system.

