4.2.1 Rescue medication, emergency procedures, and additional treatments

In this trial clopidogrel, ticagrelor and ASA are considered a NIMP. This means that in the event of a serious adverse event (SAE), the Investigator will assess the causal relationship of the SAE to the NIMP. Further details regarding SAE reporting can be found in [Section 5.2.2.3](#).

The Investigator is responsible for ensuring that procedures and expertise are available to cope with medical emergencies that may occur during the study.

Proprietary confidential information.

© 2016 Boehringer Ingelheim International GmbH or one or more of its affiliated companies. All rights reserved.

This document may not - in full or in part - be passed on, reproduced, published or otherwise used without prior written permission.

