4.2.2 Restrictions

4.2.2.1 Restrictions regarding concomitant treatment

Corticosteroids or NSAIDs may be used if clinically indicated according to current treatment guidelines but it is strongly recommended to avoid these if possible. It should be noted that the use of any of these agents with warfarin or dabigatran etexilate is likely to increase the risk of bleeding.

The following treatments should not be taken during the active treatment phase of the trial:

1. Treatment with ticlopidine or prasugrel
2. Fibrinolytic agents (see [Section 4.2.1.4](#) for exception)
3. GPIIb/IIIa antagonists (e.g. abciximab, tirofiban)
4. Treatment with systemic ketoconazole, itraconazole, posaconazole, cyclosporine, tacrolimus, dronedarone and rifampicin, phenytoin, carbamazepine or St. John's Wort
5. Dipyridamole, rivaroxaban, apixaban and edoxaban, or other oral anticoagulants (e.g. VKAs)
6. ASA - except where specified in the protocol for patients randomised to the warfarin arm or in both treatment arms after 12 months of treatment if clopidogrel or ticagrelor is switched to ASA ($\leq 100\text{mg q.d.}$) at Investigator discretion. The patients should be advised to not use additional ASA-containing over-the-counter medications.

The Investigator is alerted to the use of concomitant administration of moderate to strong P-gp inhibitors (e.g. such as amiodarone, verapamil, quinidine, nelfinavir, posaconazole, ritonavir, saquinavir and tipranavir+ritonavir or lopinavir+ritonavir) or P-gp inducers in this study due to a potential risk of higher or lower plasma levels of dabigatran and consequent exaggerated or reduced pharmacodynamic effect of dabigatran etexilate (notably bleeding risk). Concomitant use of such drugs is not prohibited in this study *per se* (except for treatment with ketoconazole, itraconazole, posaconazole, cyclosporine, tacrolimus, dronedarone, rifampicin, phenytoin, carbamazepine or St. John's Wort), but should be used with caution or, at Investigator discretion, switched to a suitable alternative.

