10.1.3 Bridging Therapy (e.g. for temporary interruptions of study drug due to interventions)

The use of bridging therapy depends on the thromboembolic risk status of the patient and the length of the planned interruption. It is at the discretion of the investigator whether to use a parenteral anticoagulant for bridging purposes or not.

Due to the short off- and onset of action, the majority of interventions in patients receiving dabigatran etexilate may not require the use of bridging therapy. If bridging therapy is deemed necessary for patients in the dabigatran etexilate arm, it is recommended to wait 12 hours after the last dose before switching from dabigatran etexilate to a parenteral anticoagulant.

Patients in the warfarin arm should be treated at the discretion of the investigator. In general, a parenteral anticoagulant may be considered when the INR is below the target INR. For recommendations how to switch back to study drug (dabigatran etexilate or warfarin) see Sections [10.1.1](#) and [10.1.2](#).

Proprietary confidential information.

© 2016 Boehringer Ingelheim International GmbH or one or more of its affiliated companies. All rights reserved.

This document may not - in full or in part - be passed on, reproduced, published or otherwise used without prior written permission.

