D3.1	Mandatory medication not taken per protocol (ASA)	ASA not taken for the first month for warfarin patients with a BMS or for the first three months for patients with a DES as indicated on the Trial Medication Compliance eCRF page (exclude if at least one visit is ticked "No").	PPS, but only from start of non-compliance onwards
D3.2	Mandatory medication not taken per protocol (clopidogrel/ticagrelor)	Clopidogrel/ticagrelor non-compliance during the first 12 months of treatment as indicated on the Trial Medication Compliance eCRF page (exclude if at least one visit is ticked "No").	PPS, but only from start of non-compliance onwards
G	Trial Specific Protocol Violations		
G1	Patient not withdrawn from treatment if CrCl drops to <30mL/min at two different occasions during the trial	As per study protocol, this only applies to patients randomised to dabigatran etexilate.	PPS

KEY: PPS – Per Protocol Set

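### Does leaving the meaning of study drug unstated in the third CRNMBE criterion tilt the primary bleeding endpoint towards one arm?

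*Protocol*

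**What the plan says.** Protocol 5.2.2.1 classes an overt bleed that falls short of major as a CRNMBE if it leads to at least one of three things: hospital admission, physician-guided medical or surgical treatment, or "A physician guided change, interruption¹ or discontinuation of study drug". A footnote limits the third: "Interruption of study drug (more than omitting one dose) due to the bleeding event". Neither the criterion nor the footnote names the drugs.

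SAP 5.1 refers to the protocol for the ISTH criteria and to the Adjudication Charter for the adjudication criteria. Protocol 3.1.1 says the charter will hold the detailed definition of each endpoint. The charter is not among the documents. Under SAP 7.4 only events confirmed by the blinded adjudication committee are analysed.

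On aspirin, Protocol 4.1.1 gives it to patients randomised to warfarin "for either one month in patients with a BMS and for three months in patients with a DES". The list of treatments to be avoided in Protocol 4.2.2.1 includes "ASA - except where specified in the protocol for patients randomised to the warfarin arm", with a second exception in all arms once clopidogrel or ticagrelor is switched to aspirin after 12 months. Clopidogrel or ticagrelor is given to everyone for at least 12 months (Protocol 4.1.4).

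**The concern.** The third criterion turns on what an unblinded physician does. If study drug means only dabigatran or warfarin, a bleed answered solely by stopping aspirin is not a primary event, unless the committee regards the stop as medical treatment. If study drug includes aspirin, that bleed counts. During the first one or three months only warfarin patients should be taking aspirin, so the choice of reading seems to move events in one arm. The narrow reading would raise the hazard ratio against dabigatran; the wide one would lower it.

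Steps 1, 2, 4 and 6 of the hierarchy all test this endpoint, and no analysis visible in SAP 7.4 varies the criterion.

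Two related terms also look uneven. Missing more than one dose is a shorter gap on twice-daily dabigatran than on once-daily warfarin. A change of study drug is undefined and may be easier to meet on a titrated drug.

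**Working it through.** **Which reading the text supports**

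For the narrow reading (randomised anticoagulant):
- Protocol 10.1.3 refers to "how to switch back to study drug (dabigatran etexilate or warfarin" and names nothing else.
- Protocol 4.2.1: "In this trial clopidogrel, ticagrelor and ASA are considered a NIMP". Protocol 4.1.4 calls these drugs background medication, and Protocol 4.1.8 gives them separate traceability rules.
- Protocol 4.2.1.5 stops study drug when another anticoagulant is needed, while allowing aspirin and clopidogrel. There the term is set against the antiplatelets.
- SAP 6.1 builds its treatment periods on the randomised study drug.

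For the wide reading:
- Protocol 3.3.4.1 mentions "concomitant drugs that interfere with the investigational product or other study medication(s". Protocol 4.1.1 calls dabigatran the investigational product and warfarin the comparator, so warfarin fits the second term. Aspirin is not named.
- SAP Table 6.2: 1, code D3.1, takes "ASA not taken for the first month for warfarin patients with a BMS or for the first three months for patients with a DES" from an eCRF page titled for trial medication compliance. The same table files that code under category D, concomitant medication, and not under category C, trial medication and randomisation.

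**Reproducing the plan's figures**

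Inputs from Protocol 7.2 and 7.6: 334 events per pair, margin 1.38, one-sided 0.025, 14% with an event at one year, 834 patients per arm, follow-up 6 to 30 months. Assumed: true hazard ratio 1.00 and constant hazard.
- Power = Φ(ln 1.38 × √334/2 − 1.96) = Φ(0.3221 × 9.138 − 1.96) = 83.7% (plan: 83.6%).
- Hazard = −ln 0.86 = 0.1508 per year. Events per arm = 834 × [1 − (e^(−0.5×0.1508) − e^(−2.5×0.1508))/(2 × 0.1508)] = 166 (plan: 167).
- Warfarin-arm events in month 1: 834 × (1 − e^(−0.1508/12)) = 10. In months 1 to 3: 834 × (1 − e^(−0.1508/4)) = 31. If the hazard in the first three months is twice the later one, with 14% at one year kept: 17 and 49.

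**If only warfarin bleeds moved**

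Let m be the warfarin bleeds that count on the wide reading only; m is assumed.
- Non-inferiority error on the wide reading, if the narrow-reading hazard ratio is 1.38: Φ(ln(1 + m/167) × 9.138 − 1.96).
- Power on the narrow reading, if the wide-reading hazard ratio is 1.00: Φ((ln 1.38 + ln(1 − m/167)) × 9.138 − 1.96).

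| m | Error (nominal 2.5%) | Power (base 83.7%) |
|---|---|---|
| 5 | 4.6% | 76.0% |
| 10 | 7.7% | 66.2% |
| 17 | 14.1% | 50.1% |

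The value m = 17 is 17/31 = 55% of the warfarin events expected in months 1 to 3, or 17/49 = 35% with the doubled early hazard. Each such bleed would need an aspirin stop as its sole response: no admission, no physician-guided treatment, no warfarin change or hold.

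**If the wide reading is applied consistently**

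Aspirin, clopidogrel and ticagrelor share one sentence in Protocol 4.2.1, and SAP codes D3.1 and D3.2 draw on the same eCRF page. Grounds that bring in aspirin therefore bring in the P2Y12 inhibitor in every arm. Suppose 17 warfarin and 10 dabigatran bleeds move (assumption):
- Error: Φ((ln(1 + 17/167) − ln(1 + 10/167)) × 9.138 − 1.96) = Φ(0.0388 × 9.138 − 1.96) = 5.4%.
- Power: Φ((0.3221 − 0.1074 + 0.0618) × 9.138 − 1.96) = 71%.

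If equal proportions move, the hazard ratio does not change.

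**The interruption rule**

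A one-day hold omits two dabigatran doses, which counts, but one warfarin dose, which does not. The rule can only add dabigatran events, which is conservative for Steps 1, 2, 4 and 6. It also has a pharmacological basis in the protocol: Section 4.2.1.3 puts plasma levels at about 25% of steady-state trough after two omitted doses with normal renal function, and Section 10.1.3 notes the drug's short offset. A common limit in hours would equate gaps with different effects on anticoagulation.

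**The case for a change.** The best case for action is that an undefined term sits inside the primary endpoint and mandated aspirin exposure is one-sided. Blinding the committee cannot remove a difference that lies in the recorded action itself. Results near a boundary are fragile: with 148 v 186 events the upper bound is 0.987, and removing three warfarin events takes it to 1.004. A sentence in the SAP and a descriptive repeat analysis look cheap.

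Part of this stands. The criterion does not name the drugs. During the aspirin window a wide reading would probably move more warfarin bleeds than dabigatran bleeds. No visible analysis tests the reading.

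The rest is weaker:
- A result whose bound is 0.987 would be tipped by almost any reclassification, and hazard ratios of that order are not in the documents.
- The repeat analysis is not free. The final SAP is dated 9 June 2017, after the final-visit window that closed on 30 April 2017, so the committee would have to re-read settled cases. The interruption reasons in SAP 7.3 cover study medication, and no visible text says the reason for stopping aspirin is recorded.
- SAP 7.8.5 already analyses ISTH major bleeding and ISTH total bleeding by the primary methods. Neither depends on the third criterion, and they lie on either side of the composite, although outside the hierarchy.
- SAP 7.8 places the bleeding analyses in SAP 7.6, which is not visible, so more may be planned.

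**Conclusion.** No change to the plan is needed. The missing definition is a gap that the adjudication committee can fill sensibly: the protocol uses study drug for dabigatran or warfarin, treats aspirin and the P2Y12 inhibitors as background medication, and hands detailed criteria to the charter. The claim that the reading moves events in one arm only does not hold, because the wide reading reaches drugs taken in all arms and aspirin is allowed in all arms after month 12.

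The one-sided calculation gives an error of 4.6% to 14.1% and power of 76.0% to 50.1% for 5 to 17 moved bleeds. With an assumed partial offset of 10 dabigatran bleeds against 17, these become 5.4% and 71%. All of this rests on assumed counts; the documents give neither the number of such bleeds nor the net direction with any size.

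The dose-based interruption limit is a defensible trade-off that works against dabigatran. An undefined change of dose may work the other way, and the documents allow no estimate of either. This conclusion would weaken only if the charter, or the committee's practice, proved to count aspirin stops while ignoring P2Y12 stops. Nothing in the documents suggests that.
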